
### 6.3 Risk minimization

The risks of participation are minimal. The primary risk is breach of confidentiality. The PI and all key personnel participating as research study staff in the proposed project have completed and will continually maintain requirements for certification

**PROTOCOL TITLE:****ENGAGED2: ExperiEnces with MammoGrAphy screeninG and brEast Density 2**

in Human Subject Research Protection. Research team conference meetings/calls will be conducted to discuss the course of the research and provide a forum for identifying and discussing any adverse events. A specific protocol will be in place to provide study participants experiencing distress with appropriate referrals for psychological counseling, whether or not this distress is connected with their research participation.

**6.4 Measures are summarized in Table 1:**

Study Measures			
Variable	Timepoint		
	Baseline	6-wk.	12-mo.
Sociodemographics	X		
Medical/Screening Variables	X		X
Plan coverage	X		X
Health-system level variables	X		X
Outcomes			
Healthcare utilization			
Chemoprevention uptake	X		X
MRI uptake	X		X
Mammography uptake	X		X
Healthcare utilization	X		X
Patient-reported outcomes			
Distress (IES)	X	X	X
Patient-provider discussion	X		X
Mediators			
Mammography/CBE intentions	X	X	X
Chemoprevention intentions		X	X
MRI intentions		X	X
Awareness of breast cancer risk	X	X	X
Perceived breast cancer severity	X	X	X
Perceived breast cancer risk	X	X	X
Breast cancer worry	X	X	X
Self-efficacy: Chemoprevention, MRI		X	X
Response cost: Chemoprevention, MRI		X	X
Response efficacy: Chemoprevention, MRI		X	X
Moderators			
Health literacy (Chew et al.)	X		
eHealth literacy (eHEALS)	X		
Numeracy (SNS)	X		

**7.0 Data and Specimen Banking\***

**7.1 Data will only be shared as requested through the NIH Resource**

**Sharing Plan Requirement.**

We will make de-identified data available by request to investigators not associated with the study. Priority for sharing of data will be given to junior faculty and/or faculty interested in questions related to translational science. We see this study as an important resource for examining issues related to clinical integration of breast density. Any requests for data from non-study investigators will be reviewed

PROTOCOL TITLE:

ENGAGED2: ExperiEnces with MammoGrAphy screeninG and brEast Density 2

by the investigative team to ensure that it does not conflict with planned analyses, is otherwise respectful of the study participants, and complies with all relevant IRB and HIPAA regulations.

We will make study data available to other investigators under data sharing agreements that ensure that (1) the data will be used only for research purposes, (2) no individual participant's de-identified data will be disseminated, (3) the data will not be used to identify an individual participant, (4) data will be protected under appropriate security measures including encryption and password protection, and (5) the data will be destroyed or returned to us upon completion of relevant analyses. If appropriate, we will also determine whether at least one study investigator should be involved scientifically in any projects that result from data sharing requests.

**8.0 Sharing of Results with Subjects\***

8.1 Study results will be shared with participants at the end of the study.

**9.0 Study Timelines\***

- 9.1 Phase 1: Participants will be enrolled in the study for a single interview or focus group, approximately 2 hours once.
- 9.2 Phase 2: Participants will be enrolled in the study for 12 months, with 3 distinct events: baseline survey, 6-week follow-up survey, 12-month follow-up survey. Total combined time commitment is approximately 3 hours or less over the course of the year.
- 9.3 Total anticipated study duration is 4 years, including subject follow-up and data analysis.

**10.0 Inclusion and Exclusion Criteria\***

10.1 Study staff will screen eligibility prior to recruitment.

10.2 Inclusionary Criteria:

**Focus Group:** Women, aged 40-69, who are enrolled at Kaiser Permanente Washington at least one year prior to mammogram, receive care in the greater Seattle area and have had a negative mammogram (BIRADS 1 or 2 assessment) as part of their routine care within the past 6 months, no prior breast cancer, invasive or DCIS (ever), no prior LCIS diagnosis, no BRCA mutation carriers or genetic counseling visits.

**Beta/Usability testing:** Women, aged 40-69, who are enrolled at Kaiser Permanente Washington, receive care in the greater Seattle area and have had a negative mammogram (BIRADS assessment of 1 or 2) as part of their routine care. Utilizing the Breast Cancer Surveillance Consortium Risk Calculator (<http://tools.bscs.org>)

PROTOCOL TITLE:

ENGAGED2: ExperiEnces with MammoGrAphy screeninG and brEast Density 2

scc.org/BC5yearRisk/), women will have high 5-year (>1.66%) risk for breast cancer and high breast density (heterogeneously or extremely dense). Women will have been enrolled for year prior to the mammogram at Group Health.

**Randomized Controlled Trial:** Women, aged 40-69, who are enrolled at Kaiser Permanente Washington, and have had a negative mammogram as part of their routine care. Utilizing the Breast Cancer Surveillance Consortium Risk Calculator (<http://tools.bcs-scc.org/BC5yearRisk/>), women will have either (a) an intermediate 5-year risk (>1.67%-2.49%) and extremely dense breasts or (b) a high 5-year risk ( $\geq 2.50\%$ ) and either heterogeneously dense or extremely dense breasts. Women must also have a valid email address.

Exclusionary Criteria:

Exclusion criteria include not able to speak and read English; not able to physically attend the focus group location and time. Exclusion criteria for beta/usability testing and the trial include not able to speak and read English; history of LCIS, prior cancer diagnosis (including DCIS), known BRCA1/2 family mutation, or previous receipt of cancer genetic counseling. While usability testing participants will need to attend in person, beta testing and trial participants will not be required to physically attend to participate. They will also be excluded if they have indicated they do not want to be contacted for research, if they participated in our previous intervention development activities, or if they died or dis-enrolled from health plan between mammogram and start of recruitment.

## 11.0 Vulnerable Populations\*

11.1 Pregnant women will not be excluded from this study if they are otherwise eligible to participate. We will ensure that all participants are able to provide meaningful informed consent such that they will be asked to repeat back the purpose of the study after a member of the study team has explained the study verbally and gone over the written informed consent.

Students will not be excluded from this study if they are otherwise eligible to participate. We will ensure that all participants are able to provide meaningful informed consent such that they will be asked to repeat back the purpose of the study after a member of the study team has explained the study verbally and gone over the written informed consent.

Women who are economically or educationally disadvantaged will not be excluded from this study if they are otherwise eligible to participate. We will ensure that all participants are able to provide meaningful informed consent such that they will be asked to repeat

PROTOCOL TITLE:

ENGAGED2: ExperiEnces with MammoGrAphy screeninG and brEast Density 2

back the purpose of the study after a member of the study team has explained the study verbally and gone over the written informed consent.

In addition, although we will be providing incentives for participation in the form of a gift card, the amount of the incentives are not so large as to be coercive. Study related materials will be written at an 8th grade level.

## 12.0 Local Number of Subjects

- 12.1 Total number of subjects to be accrued locally: 10
- 12.2 Total number of subject to be accrued nationally: 1300

## 13.0 Recruitment Methods

### 13.1 Recruitment Procedures

**Focus Group:** The Kaiser Permanente Washington programmer will identify patients using Kaiser Permanente Washington administrative data, who are age 40 – 69, receive care in the greater Seattle area and have had a negative screening mammogram as part of their routine care within the past 6 months. From this pool we will select a sample for outreach, oversampling to include diversity in race, ethnicity, and education level. Kaiser study staff will mail potential participants a letter that invites them to participate in a 2-hour group discussion. The letter will give a telephone number to call if the person wants to participate or does not want to be contacted further. Kaiser study staff will follow-up with a telephone call to individuals who call to say they are interested to confirm eligibility and give more information about the study. The study staff will mail a confirmation letter to participants who are confirmed, along with a copy of the consent form to review prior to attending the focus group.

**Usability Testing:** The Kaiser programmer will identify patients with Kaiser Permanente Washington administrative data using the following criteria: females aged 40-69 who have received a routine mammogram and are at-risk for breast cancer. From this pool, we will select a sample for outreach, oversampling to include diversity in race, ethnicity, and education level. Kaiser study staff will mail potential participants a letter that invites them to participate in the study. The letter will give a telephone number to call if the woman wants to participate or does not want to be contacted further. Kaiser study staff will follow-up with a telephone call to individuals who have not actively declined to confirm interest and eligibility and give more information about the study. The study staff will mail a confirmation letter to participants who are confirmed, along with a

PROTOCOL TITLE:

ENGAGED2: ExperiNces with MammoGrAphy screeninG and brEast Density 2

copy of the consent form to review prior to attending usability testing session.

**Beta Testing:** Women will be recruited from the Kaiser Permanente Washington in Seattle, WA, using the same means as the usability testing.

Kaiser study staff will mail eligible patients a letter inviting them to participate in the beta testing of intervention procedures. Beta testing intervention procedures include: 1. Baseline phone interview, 2. Intervention website navigation, and 3. Semi-structured feedback interview and survey after 2 weeks of beta testing. The invitation letter will provide a telephone number for Group Health to call if participants would like to first ask questions about the study, call to consent and schedule their participation, and/or who do not want to be contacted further.

**RCT:** Kaiser will recruit women as they receive a negative screening mammogram. Patients routinely complete a scantron patient risk factor questionnaire at the time of the mammogram as part of Kaiser's membership in the BCSC. A Kaiser study programmer who works with the BCSC will use these risk factor data and density readings to identify eligible patients. Women will have either (a) an intermediate 5-year risk ( $>1.67\%-2.49\%$ ) and extremely dense breasts or (b) a high 5-year risk ( $\geq 2.50\%$ ) and either heterogeneously dense or extremely dense breasts. Women must also have a valid email address. Patients will be recruited via an introductory letter from the study team. This letter will notify them of their density status and introduce them to the study. Kaiser Survey Research Program will use standardized methodology for proactive telephone contact and verbal consent.

13.2 Recruitment materials are attached with the application.

13.3 Subject compensation

Focus group: \$50 cash upon completion of the focus group

Beta and usability testing: \$20 cash upon completion of the session

RCT: \$20 cash upon completion of each interview

#### **14.0 Withdrawal of Subjects\***

Participants will be informed that they can withdraw from the study at any time. We will track the number of eligible participants that withdraw from the study. Reasons participants may withdraw or dropout of the study include lack of time and not being interested in participating in research related to breast density and mammography.

When a participant drops out, if she indicates that we cannot use the data collected thus far, then we will destroy it and not include it in analyses. If the

PROTOCOL TITLE:

ENGAGED2: ExperiEnces with MammoGrAphy screeninG and brEast Density 2

participant simply no longer wants to participate but does not request that we do not use the existing data, then we will use the data already collected.

## 15.0 Risks to Subjects\*

*15.1* The primary sources of risk concerns data privacy, confidentiality, and psychological discomfort. There are few psychological risks to completing cognitive, decision making, and psychological assessments. However, surveys and interviews may contain questions that make participants feel uncomfortable or bring up unwanted thoughts or feelings. All participants will be informed in advance of participation and each data collection opportunity that any questions that make them feel uncomfortable may be skipped or ignored.

The risk of gathering social, behavioral, and medical information is also present.

There is some risk for breach of confidentiality. However, we have taken multiple steps to ensure this risk is very low. Only key staff members will have access to individually identifiable private information about participants, including the principal investigator, the project coordinator, and research assistants. We also developed a rigorous data management plan to reduce this risk.

## 16.0 Potential Benefits to Subjects\*

*16.1* There is no direct benefit to subjects. It is possible that participants may derive benefit from taking part in the intervention and surveys. Participants will be informed about the results of the study.

## 17.0 Data Management\* and Confidentiality

### *17.1 Data Analysis Plan, including statistical procedures and power analysis*

Phase 1: Analysis of focus group data and most beta and usability testing will be done using qualitative methods and therefore is not subject to statistical considerations. Quantitative data in the beta and usability testing will use t-tests and Chi-square tests to examine differences, with a p-value of .05.

Phase II: We will calculate descriptive statistics for all variables. We will assess the quality of the data and evaluate the extent of missing data. If needed, we will address missing data issues by using multiple imputation methods; we will generate 10 multiple imputed datasets, analyze each separately, and then combine results across the 10 datasets. All statistical analyses will be performed as intention-to-treat (ITT) analyses. Given our use of administrative data to measure our primary outcomes, we will retain all women who consented and completed the baseline (N=1250). Assuming a 5% attrition rate from Group Health during the 12 months, we will use 1188 participants for our primary analyses (594/arm). For patient reported outcomes, we anticipate 10% attrition at 6 weeks and 10% attrition at 12 months, leaving 506/arm at 12 months. We will evaluate the associations

PROTOCOL TITLE:

ENGAGED2: ExperiNces with MammoGrAphy screeninG and brEast Density 2

between baseline variables, mediating variables assessed at 6 weeks, and 12 month outcomes. For categorical variables we will use Chi-Square tests or Fisher's exact tests if needed, while for continuous variables we will use Student t-tests or Wilcoxon-Mann-Whitney tests. Any variable that exhibits a  $p < .10$  association with outcomes of interest will be subsequently controlled for in analyses. We will assess attrition rates and subgroup effects over the short- and longer-term.

Power calculations assume a two tailed  $\alpha = .05$  and  $N = 1188$  at 12 months (594/arm) for primary utilization outcomes of chemoprevention and MRI; calculations for patient-reported outcomes will assume  $N = 1012$  at 12 months (506/arm). To account for clustering by provider, we calculated effective sample sizes assuming an average cluster size of 11 patients/provider and intraclass correlation coefficient of 0.02. This reduces the sample size by a factor of 1.2, leaving effective sample sizes of 990 for utilization outcomes and 842 for patient-reported outcomes. We employ generalized estimation equations (GEE) methods with exchangeable working correlation structure to analyze clustered data.

Assess intervention effects on uptake and distress. 1a: Compared to UC, women in the PW arm will have higher rates of MRI and chemoprevention uptake at 12-months post-randomization. We will use logistic regression models with GEE to account for patients' clustered binary outcomes within their providers. We will use 2 separate logistic regression models for each binary outcome: chemoprevention and MRI uptake. These models will include intervention (PW vs. UC) as the main predictor, and baseline covariates as controlling variables. Given the effective sample size of 990, we provide a range of effect sizes that correspond to statistical power ranging from 80% to 99% in Table 5. UC rates are based on published uptake of chemoprevention and breast MRI. 1b: The intervention will not lead to increased distress compared with UC. To demonstrate that the PW arm does not result in greater distress than UC, we will test for noninferiority by constructing a one-sided 97.5% confidence limit for the adjusted (for baseline distress) mean difference between arms. Noninferiority will be demonstrated when the one-sided 97.5% confidence limit does not cross the noninferiority limit of 3 points. We arrived at this noninferiority limit based on outcomes among patients at increased cancer risk. Given the effective sample size of 842 we will have 80% power to conclude non-inferiority assuming a SD of 15.3 points. This reflects an extremely small effect size of  $< 0.20$ . 1c: Women in the PW arm will have higher rates of follow-up with providers to discuss MRI/chemoprevention. 1d: Women in the PW arm will have higher rates of mammography maintenance. We will use the approach in 1a for 1c and d.

Identify mediators/moderators of intervention impact on uptake. 2a: Consistent with PMT, higher uptake of risk management in the PW arm will be mediated by increased perceptions of cancer threat (greater awareness of personal risk, higher perceived breast cancer risk, severity and worry) and stronger coping appraisals (higher response efficacy, lower response cost for preventive services; higher self-efficacy). To increase power we will use the product of coefficients method to

PROTOCOL TITLE:

ENGAGED2: ExperiencEs with MammoGrAphy screeninG and brEast Density 2

evaluate mediation effects. Using logistic regression models with GEE we will estimate the standardized coefficients relating each mediating variable (e.g. worry) to the chemoprevention and MRI uptake outcomes ( $\beta$ ), and the standardized coefficients relating the intervention (PW vs. UC) to the mediating variables ( $\alpha$ ). These models will control for the baseline measurement of the mediator variable and also other baseline covariates. We will then calculate each mediated effect as the corresponding product of these coefficients ( $\alpha\beta$ ) with its standard error and 95% confidence interval estimated as described by MacKinnon. Effect sizes of 0.14, 0.39 and 0.59 for the coefficient parameters are considered “small”, “medium” and “large” respectively. We will be able to detect a mediation effect (coefficient product) of small size (with coefficient product parameters  $\alpha = 0.14$ ,  $\beta = 0.14$ ) at >95% power for each mediator, given our total effective sample size of 842.

Given our incorporation of intervention elements supporting patient comprehension, values clarification and communication, we anticipate that PW participants will have similar rates of risk management regardless of literacy/numeracy level. In contrast, we expect lower uptake of risk management options among UC participants with lower literacy/numeracy. However, even with our large sample, we are underpowered to detect this subtle moderation effect. Therefore, we will examine these relationships in exploratory subgroup analyses. We also will assess the robustness of outcomes across patient subgroups using additional, exploratory moderation analyses. Given our individual focus, we will examine adoption by patients, but explore whether effects are moderated by clinical variables (i.e., mammography facilities, primary care clinic home).

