### 2.2 Hypotheses/Research questions.

- 1a: Compared to UC, women in the PW arm will have higher rates of MRI and chemoprevention uptake at 12-months post-randomization.
- 1b: The intervention will not lead to increased distress compared with UC.
- 1c: Women in the PW arm will have higher rates of follow-up with providers to discuss MRI/chemoprevention.
- 1d: Women in the PW arm will have higher rates of mammography maintenance.
- 2a: Consistent with PMT, higher uptake of risk management in the PW arm will be mediated by increased perceptions of cancer threat (greater awareness of personal risk, higher perceived breast cancer risk, severity and worry) and stronger coping appraisals (higher response efficacy, lower response cost for preventive services; higher self-efficacy).

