#### 4.0 Study Endpoints\*

- 4.1 *Primary Endpoint:* 12 month interview and appointment and pharmacy data for endpoints of chemoprevention, screening and physician appointments.
- 4.2 *Secondary Endpoints:* 12 month cancer-related distress, mammography maintenance, healthcare utilization
- 4.3 *Safety Endpoints:* Safety endpoints have not been established as this is a minimal risk study.

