##### 5.2 *Phase 2: Randomized Control Trial*

PROTOCOL TITLE:

ENGAGED2: ExperiEnces with MammoGrAphy screeninG and brEast Density 2

Potentially eligible patients will be identified, recruited, and enrolled following a negative screening mammogram and review of a routine risk factor questionnaire administered at the time of the mammogram.

At the conclusion of consent, a baseline survey (T1) will be administered. At the conclusion of the baseline interview, participants will be randomized in equal numbers to personalized web site (PW) or usual care (UC; ACS website) via computer-generated random numbers.

Participants will be notified after randomization that they will receive instructions in approximately two weeks for them to log into the website. Women will receive login information that will take them to UC or PW. Participants will be contacted for follow-up interviews at 6-weeks (T2) and 12-months (T3).

**Control (UC) Arm:** Participants randomized to UC will receive a login that will allow them to access the UC portal and the American Cancer Society website. Our creation of a login portal to a public site will allow us to track who viewed the website, but will not allow for complete utilization data. Participants will be told that this website covers many topics that are pertinent to their health. While the participants will be able to examine any part of the website, they will be asked to review the following sections: Medicines to Reduce Breast Cancer Risk, Breast Cancer Early Detection, and the Prevention Checklist for Women. Therefore, UC participants will have the opportunity to receive much of the same general information as PW participants.

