***Non-English Speaking Subjects***

- n/a

***Waiver or Alteration of Consent Process (consent will not be obtained, required information will not be disclosed, or the research involves deception)***

- We are requesting a limited HIPAA waiver to support recruitment. All information obtained for individuals who are not retained as participants will be destroyed.
- We are opting for an online consent as the primary means of consent for anyone using the website (PW or UC) as we have concerns with potential participants accessing and using the intervention website in advance of returning signed written consent and possibly without ever returning the signed written consent. We want to be sure there is clear communication regarding the elements of consent and have documentation of consent before participants enter into the tailored information of the website. Written paper consent will be used as a back-up for those who do not log on. Those who do not return this paper consent will not be contacted for the 12 month and will be purged from the dataset.

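### The distress non-inferiority test (1b) is planned by ITT alone, so it can support a claim about offering the website but not about using it

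*Combined protocol and SAP*

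**What the plan says.** Section 2.2 sets the hypothesis: "1b: The intervention will not lead to increased distress compared with UC". Section 4.2 lists distress among the secondary endpoints, measured at 12 months. Under 1b in section 17.1, "we will test for noninferiority by constructing a one-sided 97.5% confidence limit for the adjusted (for baseline distress) mean difference between arms", and "Noninferiority will be demonstrated when the one-sided 97.5% confidence limit does not cross the noninferiority limit of 3 points". The same section gives the power: "Given the effective sample size of 842 we will have 80% power to conclude non-inferiority assuming a SD of 15.3 points".

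Section 17.1 also fixes the analysis principle for the whole trial: "All statistical analyses will be performed as intention-to-treat (ITT) analyses". It names no users-only, per-protocol or complier analysis of distress.

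Non-use is provided for elsewhere. Section 6.2 (RCT Trial) has logins tracked and women prompted. In section 22.0, under the waiver or alteration of consent, "Written paper consent will be used as a back-up for those who do not log on". Sections 6.2 and 22.0 add that women who do not complete consent are not contacted at 12 months and are purged.

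Usage data will exist. Section 6.2 (Beta Testing) describes page views, time on site and repeat logins on the intervention site, to be kept for the trial analysis. Section 5.2 says the usual-care (UC) portal "will allow us to track who viewed the website", although without full usage detail.

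**The concern.** One analysis rule serves hypotheses that point in opposite directions. For 1a, 1c and 1d, which look for a difference, women who never open the site make ITT conservative. For 1b, which looks for the absence of a difference, the same women help the claim succeed: a woman who has not seen the PW content cannot be distressed by it, so her presence draws the arm means together.

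This matters because 1b is the only hypothesis about harm, and section 4.3 sets no safety endpoints. Section 3.0 presents keeping distress from rising as part of the purpose of the trial. Hypothesis 2a expects the site to work partly by raising perceived risk and worry, so distress among users is a foreseeable effect. A reader of the results will want to know about women who used the tool, and the plan pre-specifies nothing that answers this.

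**Working it through.** **Inputs from section 17.1.** SD 15.3; margin 3; one-sided 97.5% limit; 506 women per arm with 12-month interviews; 11 patients per provider; intraclass correlation 0.02; effective N 842, or 421 per arm.

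**Reproducing the plan's figure.**
- Design effect: 1 + (11 − 1) × 0.02 = 1.2. Then 1012 / 1.2 = 843, against 842 stated.
- Standard error: SE = 15.3 × √(2/421) = 1.0545 points.
- Power at zero difference: Φ(3/1.0545 − 1.96) = 81.2%. Exactly 80% would need 409 per arm. The stated 80% is confirmed.
- To succeed, the observed difference must be below 3 − 1.96 × 1.0545 = 0.93 points.

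**Dilution.** Let L be the share of PW women in the 12-month analysis who logged in, and D the true increase in distress among them. Assume no effect in PW women who never logged in. Then:
- the ITT difference is L × D;
- the probability of declaring non-inferiority is Φ((3 − L × D)/1.0545 − 1.96);
- the user effect at which the ITT difference just reaches the margin is 3/L.

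The documents give no value for L, so the range below is an assumption.

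| L | P(declare) if D = 3 | P(declare) if D = 4 | User effect when ITT difference = 3 |
|---|---|---|---|
| 100% | 2.5% | 0.2% | 3.0 |
| 90% | 4.7% | 0.6% | 3.33 |
| 80% | 8.2% | 1.6% | 3.75 |
| 70% | 13.4% | 3.8% | 4.29 |
| 60% | 20.6% | 8.2% | 5.0 |
| 50% | 29.5% | 15.6% | 6.0 |

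**What a user-level estimate can deliver.** The complier-average effect is the ITT difference divided by L. With L treated as known, its upper limit is the ITT limit divided by L, so it falls below 3 only when the ITT limit is below 3L. At zero true difference that has probability Φ(3L/1.0545 − 1.96): 73% at 90% login, 62% at 80%, 51% at 70%, 40% at 60% and 30% at 50%. A comparison of logged-in women in both arms, with 421 × L per arm, has power of 77.0%, 72.1%, 66.3%, 59.6% and 52.1% at the same shares.

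**The case against.** Four arguments on the other side have force.

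- **The planned test is valid for the question it literally asks.** 1b compares arms as randomised. For the effect of offering the site, ITT holds the one-sided error at 2.5%. A reader might infer from the table that the planned test has an inflated error rate. It does not: the larger figures apply only if the target is the effect among users, and the plan never says which effect it means. This objection stands, and it sets the form of the conclusion.
- **Not every non-logger is kept.** A reader might infer that all women who never log in dilute the comparison. Only those who return the paper consent and are then interviewed at 12 months do so. The purge removes the rest, and the prompts raise use. This stands and limits L from below, by an unknown amount.
- **The size has no anchor.** A back-up consent route is not a forecast of low use. The 50% and 60% rows illustrate what could happen and do not predict it.
- **A second hurdle would be expensive.** Requiring the complier limit as well as the ITT limit to fall below 3 would shrink the effective margin to 3L, with the power losses shown above. A reader might think the test needs such a gate. The documents do not call for one, and the cost is too high without a larger sample.

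None of this supplies the missing piece, which is a stated target for 1b and a pre-specified estimate for women who used the site.

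**Conclusion.** The concern holds in limited form. 1b is a non-inferiority claim tested by ITT only, and non-use among retained PW women favours success. A positive result would support the statement that offering the site does not raise 12-month distress by 3 points or more. Alone it would not support that statement for using the site.

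At a true user effect equal to the margin, the chance of declaring non-inferiority rises from 2.5% with full login to about 5% at 90%, 8% at 80%, 13% at 70% and 29.5% at 50%. This rests on the plan's SD and effective sample size, no effect in PW women who never log in, and an assumed login share. The actual size in this trial cannot be fixed from the documents, and they do not show that the 1b result would be wrong.

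A related inconsistency needs no assumed figure. Purging randomised women who do not complete consent (sections 6.2 and 22.0) is an exclusion after randomisation, could differ by arm, and sits badly with an ITT rule for all analyses (section 17.1). Section 17.1 keeps women who consented and completed baseline, but does not say whether that means the verbal consent before randomisation or the online or paper consent after it.

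Distress is a secondary endpoint, so this is a worthwhile improvement and not a fatal flaw.

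**What to change.** Amend section 17.1 for 1b as follows.

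1. Keep ITT as the main analysis and state that it estimates the effect of offering the site.
2. Pre-specify two supportive analyses, neither of them a second gate: (a) the complier-average effect, meaning the ITT difference divided by the PW login proportion, with its confidence limit; and (b) a comparison of women with a recorded login in each arm, adjusted for baseline IES, noting that randomisation does not protect it.
3. Report login rates and purge rates by arm.
4. If a supportive upper limit exceeds 3 points, confine the 1b conclusion to offering the site.
5. Reconcile the purge in sections 6.2 and 22.0 with the ITT statement, and define the analysis set for 12-month distress.

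ITT alone can stay for 1a, 1c and 1d.

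The cost is a paragraph of text and a little more analysis, since the logins and IES are already collected. The power of the ITT test stays at the stated 80%. The supportive intervals are wider, so with incomplete login the wording may have to be narrowed even when the site causes no distress. That is better settled before the data are seen, because a users' analysis chosen afterwards would look selective.
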